10 MEASUREMENT OF EFFECT

10.1 Venous Thromboembolism (VTE)

Cumulative incidence of venous thromboembolic events at 56 days (+/- 7 day windows) is the primary endpoint. *The composite endpoint includes any symptomatic proximal or distal lower extremity DVT, symptomatic pulmonary embolism or fatal PE diagnosed by autopsy, asymptomatic proximal DVT diagnosed by screening compression ultrasound.* All other venous or arterial events will be recorded and analyzed as secondary endpoints.

Patients presenting with symptoms compatible with DVT and/or PE will undergo radiographic imaging with either compression ultrasound, VQ lung scan, or spiral CT. Confirmed episodes of VTE will be managed by the treating physician per standard of practice.

Presence of any of the following will be considered diagnostic for a VTE:

- New non-compressibility of lower extremity deep venous segments by compression ultrasound. Distal lower extremity thrombus (lower than popliteal vein) qualifies for primary VTE endpoint only if symptomatic. All proximal thrombi qualify as primary study endpoint if identified by screening ultrasound or are symptomatic.
- Intraluminal defects in two or more views on pulmonary angiography
- Sudden contrast cut-off of one or more vessels greater than 2.5 mm in diameter on a pulmonary angiogram
- A high probability VQ lung scan showing one or more segmental perfusion defects with corresponding normal ventilation (mismatch defect)

• Abnormal spiral CT showing thrombus in pulmonary vessels (subsegmental or larger) Note: intrabdominal thrombus related to tumor compression is not considered a VTE endpoint

Other VTE

Those VTE that do not qualify for the primary endpoint such as asymptomatic distal extremity deep vein thrombosis, asymptomatic pulmonary emboli diagnosed by CT, central line-associated thrombus will be recorded and analysed as secondary endpoints.

Response Review

An independent adjudication of VTE qualifying for the primary outcome will be performed. The review committee will be comprised of two independent hematologists and a radiologist. The committee will review the medical records and radiology report for all VTE that qualify for the primary VTE endpoint. In cases where committee feels that the radiology reports or medical records are equivocal then the primary radiology images will be reviewed by an independent radiologist for adjudication.

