2.2 Coordinating Center

The Coordinating Center will assume the following general responsibilities:

- Assist in protocol development
- Maintain copies of Federal Wide Assurance and Institutional Review Board (IRB) approvals from all Participating Institutions.

- Maintain FDA or OBA correspondence, as applicable.
- Maintain updated roster of participants.
- Verify eligibility.
- Verify response.
- Oversee the data collection process from Participating Institutions.
- Maintain documentation of Serious Adverse Event (SAE) reports submitted by Participating Institutions and submit to DF/HCC Sponsor for timely review.
- Distribute adverse events reported to the DF/HCC Sponsor that fall under the DFCI IRB Adverse Event Reporting Policy to all participating investigators.
- Provide Participating Institutions with information regarding DF/HCC requirements that they will be expected to comply with.
- Monitor Participating Institutions either by on-site or virtual monitoring.
- Maintain Regulatory documents of all Participating Institutions.
- Conduct regular communications with all Participating Institutions (conference calls, emails, etc).
- Maintain documentation of all communications.
- Ensure that each Participating Institution has the appropriate assurance on file with the Office of Human Research Protection (OHRP).

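### The adjudication committee sees only VTE already classed as primary, so it can confirm or remove a primary event but has no route to recover one filed as other VTE

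*Combined protocol and SAP*

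**What the plan says.** Section 10.1 of the combined protocol and SAP makes cumulative incidence of VTE at 56 days the primary endpoint. The composite comprises symptomatic lower-extremity DVT (proximal or distal), symptomatic or autopsy-proven fatal pulmonary embolism, and asymptomatic proximal DVT found on the screening ultrasound.

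The Response Review paragraph opens with the committee's remit: "An independent adjudication of VTE qualifying for the primary outcome will be performed". It then says what the committee is sent: "The committee will review the medical records and radiology report for all VTE that qualify for the primary VTE endpoint". Images are a second step, taken only on the committee's own prompting: "In cases where committee feels that the radiology reports or medical records are equivocal then the primary radiology images will be reviewed".

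The Other VTE paragraph covers the remainder: "Those VTE that do not qualify for the primary endpoint such as asymptomatic distal extremity deep vein thrombosis, asymptomatic pulmonary emboli diagnosed by CT", together with line-associated thrombus. These are recorded and analysed as secondary endpoints, with no adjudication mentioned.

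Two classification rules matter here. For distal clots: "Distal lower extremity thrombus (lower than popliteal vein) qualifies for primary VTE endpoint only if symptomatic". For proximal clots: "All proximal thrombi qualify as primary study endpoint if identified by screening ultrasound or are symptomatic". A note in the same section also excludes intra-abdominal thrombus related to tumour compression.

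The section gives no criteria for symptomatic and names no one as responsible for sorting events into primary and other. Appendix A, section 2.2, gives the Coordinating Center a general duty, "Verify response", without describing independent review of VTE.

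**The concern.** For pulmonary embolism and distal DVT, the symptom label decides whether the event is primary. Line association and tumour compression are further grounds for filing an event elsewhere. Some of these are judgement calls. A pulmonary embolism seen on CT in a breathless patient with advanced lung cancer could reasonably be labelled either way.

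If the first label is wrong in the qualifying direction, the committee receives the event and can correct it. If it is wrong in the other direction, the event never reaches the committee, and the image re-read, which the committee triggers, cannot happen either.

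In phase III, lost true events cost power in a trial sized on about 42 primary events. In phase II there is no concurrent control, so lost events move the VTE fallback rule in one direction only, towards a favourable conclusion.

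**Working it through.** **Routes to the committee, as written in section 10.1**

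| First classification | Sent to committee? | Possible outcome |
|---|---|---|
| Qualifies as primary | Yes, with medical records and radiology report | Confirmed or removed |
| Other VTE (asymptomatic distal DVT, asymptomatic PE on CT, line-associated) | No route stated | Stays secondary |
| Work-up judged negative or equivocal | No route stated | Not counted |

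**Inputs.** Section 14.1.2.4: 11% placebo, 4% isoquercetin, 281 per arm, power 0.85, one-sided type I error 0.025. Section 14.1.1.7: promising if nine or fewer VTE in 60; a true rate of 10% is promising, and 25% is not worth pursuing. Misfiling rate: not in the documents, so 5%, 10% and 20% are assumed.

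**Reproducing the phase III sample size.** With mean rate 0.075 and difference 0.07:

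n = [1.960 × √(2 × 0.075 × 0.925) + 1.036 × √(0.11 × 0.89 + 0.04 × 0.96)]² / 0.07² = 252.7

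Continuity correction: n′ = (252.7/4) × [1 + √(1 + 4/(252.7 × 0.07))]² = 280.5, rounded up to 281. The stated figure reproduces. Exact one-sided Fisher power at 281 per arm is 0.864. Expected primary events: 281 × (0.11 + 0.04) = 42.

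**Phase III with a fraction f of true primary events misfiled in both arms.** Each rate becomes p × (1 − f).

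| f | Rates | Expected events | Exact Fisher power, 281 per arm | n per arm for 0.85 (same formula) |
|---|---|---|---|---|
| 0 | 11% / 4% | 42 | 0.864 | 281 |
| 5% | 10.45% / 3.8% | 40 | 0.843 | 297 |
| 10% | 9.9% / 3.6% | 38 | 0.818 | 315 |
| 20% | 8.8% / 3.2% | 34 | 0.763 | 357 |

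**Phase II fallback rule.** This takes the VTE counted there to be the section 10.1 endpoint. P(X ≤ 9), X binomial with n = 60:

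- True rate 10%, none missed: 92.7% (stated: at least 92%).
- True rate 25%, none missed: 4.5% (stated: less than 5%).
- True rate 25%, 10% missed: observed rate 0.25 × 0.9 = 22.5%, giving 10.5%.
- True rate 25%, 20% missed: observed rate 0.25 × 0.8 = 20%, giving 21.3%.

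**The case against.** Several points on the other side stand, and they limit what can be claimed.

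- **A reader might infer that sites make the symptom call.** The documents do not say so. They name no one, and the Coordinating Center has a general role in checking response. The gap is that responsibility is unassigned.
- **A reader might infer that the deciding classification is never adjudicated.** For each event it receives, the committee has the medical records and can overturn the symptom, location or exclusion label. Only events that are not sent go unreviewed.
- **The symptom label does not govern the whole endpoint.** Proximal DVT on the scheduled end-of-treatment ultrasound counts whatever the symptoms. If half of primary events were exposed to misfiling (an assumption), misfiling 10% of those would lose 5% overall, and power would be 0.843, close to the stated 0.85.
- **A reader might infer that one-way review itself costs power.** It does not. Adding one percentage point of false events to both arms (12% versus 5%) lowers exact power from 0.864 to 0.822, so removing false positives helps. The loss shown comes entirely from assumed misfiling upstream that the committee cannot correct.
- **A reader might infer bias in phase III.** Appendix A, section 3.7.1, blinds participants, investigators and the research team, so misfiling should be similar in both arms. Equal proportional loss leaves the relative risk unchanged.
- **The 11% control rate may already reflect some under-capture**, since it comes from a completed study of similar design. Scaling it down would then double-count. The documents do not settle this.
- **Other VTE are not discarded.** They are analysed as secondary endpoints, and total VTE is a planned secondary analysis (section 14.2).

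None of this gives the committee a route to a misfiled event. The secondary analyses would show the events but would not return them to the primary count.

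**Conclusion.** The point holds in a limited form. Adjudication as written can confirm or remove a primary event but cannot recover one filed as other VTE or left as an equivocal work-up. The plan neither assigns the first classification nor defines symptomatic. No stated figure is wrong: the phase III sample size and both phase II error rates reproduce.

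The size is conditional on misfiling rates that are assumptions throughout. In phase III the likely harm is modest loss of power, since blinding makes unequal misfiling unlikely. In phase II the effect is directional, because missed events can only favour continuation. That rule comes into play only if neither dose cohort shows a significant D-dimer reduction. The change is worth making because it is cheap and removes dependence on an unassigned, unreviewed first sort.

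**What to change.** Amend the Response Review paragraph of section 10.1 to state that:

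1. the existing committee adjudicates every reported venous event, primary and other, and every symptomatic work-up with a positive or equivocal report;
2. the committee itself assigns symptomatic or asymptomatic, proximal or distal, and exclusion status, using written criteria for symptomatic;
3. the committee is masked to arm in phase III, which the text does not currently say;
4. the committee's classification is the one used in the phase II VTE rule and the phase III primary analysis.

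The cost is one paragraph, a short adjudication definition and a larger case packet, so some extra review time. No added members or imaging are needed.

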10.2 Major Hemorrhage

Adhering to published guidelines, the criteria of major hemorrhage in non-surgical patients is: 56

- Fatal bleeding, and/or
- Symptomatic bleeding in a critical area or organ such as intracranial, intraspinal, intraocular, retroperitoneal, intra-articular or pericardial, or intramuscular with compartment syndrome, and/or
- Bleeding causing a fall in hemoglobin level ≥ 2 g/L or
- Bleeding leading to a transfusion of ≥ 2 units of packed red blood cells.

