3.2 Exclusion Criteria

Participants who exhibit any of the following conditions at screening will not be eligible for admission into phase 2 or 3 of the study.

- 3.2.1 Participants may not be concurrently receiving any other study agents.
- 3.2.2 Participants with known brain metastases should be excluded from this clinical trial because of their poor prognosis and because they often develop progressive neurologic dysfunction that would confound the evaluation of neurologic and other adverse events.
- 3.2.3 Prior history of documented venous thromboembolic event within the last 2 years (excluding central line associated events whereby patients completed anticoagulation).
- 3.2.4 Active bleeding or high risk for bleeding (e.g. known acute gastrointestinal ulcer)
- 3.2.5 History of significant hemorrhage (requiring hospitalization or transfusion) outside of a surgical setting within the last 24 months
- 3.2.6 Familial bleeding diathesis
- 3.2.7 Known diagnosis of disseminated intravascular coagulation (DIC)
- 3.2.8 Currently receiving anticoagulant therapy

- 3.2.9 Current daily use of aspirin (>81mg daily), Clopidogrel (Plavix), cilostazol (Pletal), aspirin-dipyridamole (Aggrenox) (within 10 days) or considered to use regular use of higher doses of non-steroidal anti-inflammatory agents as determined by the treating physician (e.g ibuprofen > 800 mg daily or equivalent).
- 3.2.10 Uncontrolled intercurrent illness including, but not limited to ongoing or active infection, symptomatic congestive heart failure, unstable angina pectoris, cardiac arrhythmia, or psychiatric illness/social situations that would limit compliance with study requirements.
- 3.2.11 Known intolerance of niacin or ascorbic acid (including known G6PD deficiency)
- 3.2.12 Pregnant women are excluded from this study because isoquercetin is a PDI inhibitor with the potential for teratogenic or abortifacient effects. Because there is an unknown but potential risk of adverse events in nursing infants secondary to treatment of the mother with isoquercetin, breastfeeding should be discontinued if the mother is treated with isoquercetin. These potential risks may also apply to other agents used in this study.

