5.3 Duration of Therapy

Duration of therapy will be 56 days (+/- 7 days inclusion of windows) or until one of the following criteria applies:

- Intercurrent illness that prevents further administration of treatment,
- Unacceptable adverse event(s),
- Participant demonstrates an inability or unwillingness to comply with the oral medication regimen and/or documentation requirements
- Participant decides to withdraw from the study, or general or specific changes in the participant's condition render the participant unacceptable for further treatment in the opinion of the treating investigator.
- Grade 3 or 4 hemorrhage and/or Symptomatic bleeding in a critical area or organ such as intracranial, intraspinal, intraocular, retroperitoneal, intra-articular or pericardial, or intramuscular with compartment syndrome, and/or bleeding causing a fall in hemoglobin level >2 g/L or bleeding leading to a transfusion of > 2 units of packed red blood cells.
- Proximal deep vein thrombosis or pulmonary embolism
- Condition requiring therapeutic anticoagulation
- Prophylactic heparin or low molecular weight heparin for greater than 7 consecutive days

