5.5 Criteria for Removal from Study

Participants will be removed from study when any of the criteria listed in Section 5.3 applies. The reason for study removal and the date the participant was removed must be documented in the study-specific case report form (CRF). Alternative care options will be discussed with the participant.

In the event of unusual or life-threatening complications, participating investigators must immediately notify the Principal Investigator, at

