6.2 Toxicity Management

Hemorrhage

- No modification: CTCAE grade 1
- HOLD: CTCAE grade 2 hemorrhage

Hold isoquercetin until resolution of grade 2 hemorrhage. The maximum number of consecutive days that isoquercetin can be held is 10 days before the participant must be taken off study. A participant may only hold isoquercetin for one ten day period. If a second grade 2 hemorrhage develops the participant must be taken off study.

• **Discontinue:** CTCAE grade 3-4 hemorrhage or otherwise meets criteria for major hemorrhage such as requiring transfusion 2 units PRBC, postoperative interventional radiology, endoscopic or operative intervention or life threatening consequences including spontaneous bleeding at critical site (intracranial, pericardial, retroperitoneal, intraocular, intraspinal)

In cases of suspected isoquercetin toxicity (non-hematologic only):
Grade 2: if toxicity is tolerable to patient, maintain at same dose. If toxicity is intolerable to the patient, then interrupt quercetin until recovery to grade <1
Grade 3 : interrupt until grade <1
Grade 4 : discontinue isoquercetin

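### The major-hemorrhage hemoglobin criterion in 10.2 and 5.3 carries the wrong unit: a fall of 2 g/L is only 0.2 g/dL

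*Combined protocol and SAP*

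**What the plan says.** Section 10.2 states that its definition follows published guidelines (reference 56) and lists four criteria, any one of which is enough: fatal bleeding, symptomatic bleeding at a critical site, a hemoglobin fall, and transfusion. The last two read "Bleeding causing a fall in hemoglobin level ≥ 2 g/L or" and "Bleeding leading to a transfusion of ≥ 2 units of packed red blood cells".

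Section 5.3 gives the reasons for ending therapy before day 56. Alongside grade 3 or 4 and critical-site bleeding it lists "bleeding causing a fall in hemoglobin level >2 g/L or bleeding leading to a transfusion of > 2 units of packed red blood cells". Section 5.5 adds: "Participants will be removed from study when any of the criteria listed in Section 5.3 applies".

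Section 6.2 manages bleeding by CTCAE grade:

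- Grade 1: "No modification: CTCAE grade 1".
- Grade 2: drug is held until the bleed resolves. "The maximum number of consecutive days that isoquercetin can be held is 10 days before the participant must be taken off study", and a second grade 2 bleed also takes the participant off study.
- Grade 3 or 4: drug is discontinued. The same applies to any bleed that "or otherwise meets criteria for" major hemorrhage. The examples given are a 2-unit transfusion, interventional, endoscopic or operative treatment, life-threatening consequences and critical-site bleeding.

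Major hemorrhage is a secondary objective (1.3) with its own analysis (14.2). It receives particular weight when the phase III dose is chosen (14.1.1.7), and it is named among the events that can lead to an enrollment hold and DSMB review (12.2). No section gives the hemoglobin threshold in g/dL or corrects it.

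**The concern.** A fall of 2 g/L is a very small change, yet it sits in a list whose other members are death, bleeding at a critical site and transfusion of at least 2 units. It also fits poorly with 6.2, which treats minor and moderate bleeding as reasons to continue or pause drug, not to stop it.

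The criterion is used in two ways. As an endpoint definition, it decides which bleeds enter the major-hemorrhage comparison and the safety picture that informs dose choice. As a stopping rule, it ends therapy and removes the participant. If the printed value is applied, trivial bleeds can be counted as major and some participants can lose treatment without good reason. If some sites apply the text and others silently correct it, the same bleed will be classified differently at different sites.

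**Working it through.** The threshold is a definition, so there is no calculated figure in the plan to reproduce. The check is a unit conversion, a comparison of scale, and a reading of the linked sections.

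**Inputs from the documents.** Fall of 2 g/L (10.2 and 5.3); transfusion of at least 2 units (10.2); grade tiers and discontinuation rule (6.2).

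**Assumed inputs, not in the documents.** Baseline hemoglobin 90 to 140 g/L; blood volume 4 to 6 L; rise of 5 to 15 g/L per red-cell unit.

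**1. Conversion.** 1 g/dL = 10 g/L. So 2 g/L ÷ 10 = 0.2 g/dL. If 2 g/dL was meant, the threshold is 2 × 10 = 20 g/L, ten times the printed value.

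**2. Share of baseline** (fall ÷ baseline).

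| Assumed baseline | Fall of 2 g/L | Fall of 20 g/L |
|---|---|---|
| 140 g/L | 1.4% | 14.3% |
| 120 g/L | 1.7% | 16.7% |
| 100 g/L | 2.0% | 20.0% |
| 90 g/L | 2.2% | 22.2% |

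**3. Approximate blood loss** by simple dilution (volume × fall ÷ baseline).

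| Assumed volume and baseline | Fall of 2 g/L | Fall of 20 g/L |
|---|---|---|
| 4,000 mL, 140 g/L | 57 mL | 571 mL |
| 5,000 mL, 120 g/L | 83 mL | 833 mL |
| 6,000 mL, 90 g/L | 133 mL | 1,333 mL |

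**4. Comparison with the adjacent criterion.** Two units at 5, 10 or 15 g/L each correspond to 10, 20 or 30 g/L. Divided by 2 g/L, that is 5, 10 or 15 times the printed threshold. Divided by 20 g/L, it is 0.5, 1.0 or 1.5 times. The two criteria are on one scale only if the threshold is 2 g/dL.

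**5. Fit with 6.2.** The discontinuation bullet takes in any bleed meeting the major-hemorrhage criteria, whatever its grade. A grade 1 or 2 bleed that causes a 0.2 g/dL fall therefore moves from the continue or hold tier to discontinuation. The examples in 6.2 are all far more severe than a loss of that size.

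**6. Is it a reading error from the PDF?** Unlikely. The unit appears as g/L in two separate sections, and the same text keeps mg/dl for bilirubin and creatinine in 3.1.7.

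**7. What does not depend on it.** The phase III sample size rests on VTE rates. The stopping counts in 14.1.1.5 are of attributable grade 3 or 4 events. Although the text there describes the underlying rate as one for major hemorrhages, the rule counts by grade and does not use the 10.2 hemoglobin criterion.

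**The case against.** The strongest reply is that this is a slip of the pen. Section 10.2 says it follows a published guideline, nothing suggests that the sponsor chose 0.2 g/dL, and clinicians have the 6.2 examples to show the intended severity. The reach is also limited. Bleeding must cause the fall, and these patients are receiving or scheduled for chemotherapy, so a small drop has to be attributed to a bleed before it counts. The calendar in section 9 schedules blood counts at screening, day 1, day 29 and day 56, which leaves day 29 as the only scheduled count between first dose and end of treatment. The placebo comparison is secondary, double-blind, confined to phase III, and applies one definition to both arms. Dose selection and DSMB review set no numeric threshold specific to major hemorrhage.

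The limits on reach stand. The argument that readers will correct the unit themselves does not: 6.2 imports the major-hemorrhage criteria by cross-reference, 5.3 repeats the wrong unit, and the independent adjudication in 10.1 covers VTE only.

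Four stronger readings are tempting but not supported.

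- A reader might infer that almost any bleed with a measurable hemoglobin fall would be major and end therapy, leaving the grade 1 and 2 tiers of 6.2 with nothing to govern. The documents do not show this. Bleeds with no measured or attributable fall stay under those tiers, and no bleed frequency is given.
- A reader might point to ordinary variation: with an assumed within-person standard deviation of 0.2 to 0.7 g/dL, a second reading is lower by at least 0.2 g/dL 24% to 42% of the time by chance. That is not a misclassification rate, because it ignores the requirement that bleeding cause the fall.
- A reader might treat ≥ in 10.2 against > in 5.3 as a second inconsistency. It may be an underline lost when the text was extracted, so it is not counted.
- A reader might cite exclusion 3.2.5 ("History of significant hemorrhage (requiring hospitalization or transfusion) outside of a surgical setting within the last 24 months") as proof of intended severity. It concerns prior history and serves a different purpose, so it carries little weight.

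**Conclusion.** The point holds as a unit error in 10.2 and 5.3. As printed, a bleed that causes a fall of only 0.2 g/dL is a major hemorrhage for the secondary endpoint, the dose-selection review and the DSMB trigger, and it ends therapy through 5.3, 5.5 and 6.2. The printed threshold is one tenth of the probable intended value and one fifth to one fifteenth of the adjacent 2-unit criterion on the assumed 5 to 15 g/L per unit.

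The printed unit and the conversion are certain. That 2 g/dL was meant is an inference from the scale of the neighboring criterion and from 6.2; the cited guideline was not available to confirm it. The effect on dose selection and DSMB review is a less clear safety input, not a changed numeric rule. The practical effect on participants and on the endpoint cannot be sized from the documents.

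**What to change.** Check the guideline cited in 10.2, then correct the unit in both 10.2 and 5.3. The probable value is 2 g/dL; printing it with its equivalent, 20 g/L, would prevent a recurrence. Section 6.2 needs no change: once the unit is right, its tiers and its cross-reference work as written. Section 14.1.1.5 also stays as it is.

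Make the correction now, not with the amendment that section 5 plans once the phase III decision is made, because the 5.3 stopping criteria and the 14.1.1.7 dose-selection review already apply in phase II. The cost is a wording amendment in two places. No patients, procedures or sample size are affected.
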